13.2 Sample Size Consideration

Resulting from laboratory studies conducted on the first several patients on this study, the investigative team plans to test higher doses in steroid-refractory patients with aGVHD (separating of Arms into 2A and 2B). This necessitates expanding the number of participants treated on the arms as described below:

Arm 1 Treated Patients	Arm 2A Treated Patients	Arm 2B Treated Patients
Level 1: N = 2, DLT = 0	Level 1: N = 1, DLT = 0	Level 1: N = 1, DLT = 0
Level 2: N = 2, DLT = 0	Level 2: N = 0, DLT = 0	Level 2: N = 2, DLT = 0
Level 3: N = 6, DLT = 0	Level 3: N = 3, DLT = 0	Level 3: N = 4, DLT = 0
Enroll 10 more patients Next dose level 3: N = 2	Enroll 16 more patients Next dose level 3: N = 2	Enroll 13 more patients Next dose level 4: N = 2

- The next dose was calculated with R package “dfcrm”.
- The next dose for Arm 2B was dose level 5, but restrict the dose jump, so the next dose will be dose level 4.

We now anticipate recruitment of 20 participants in each of the 3 arms to complete phase I.

In phase I, based on resources, the maximum number of allowable evaluable patients is 20 for each arm (total of 60 for all three arms). The simulations show it should be sufficient and safe to define the MTD for future efficacy trials.

For Arm 1 or 2A, if fewer than 13 patients are enrolled at the MTD, the phase II extension trial using Simon's two-stage Minmax design will require 26 patients to test the null hypothesis that the response rate at day 28 is <40% versus the alternative that the response rate is $\geq 65\%$ after assuming 80% power and a significance level of 0.05 and using a maximum of 26 patients. We will choose the rule that minimizes the expected sample size giving a true response rate equivalent to the null hypothesis. We expect that for each arm, phase I and II will require approximately 33 patients due to use of patients from the phase I trial in the phase II extension ([table 2](#) shows about 13 patients will be treated under MTD). But the sample size for each

arm could be as high as 44 when only two patients were treated at MTD in phase I. Therefore we expect the sample size of the phase I/II study for Arm 1 and Arm 2A will be 66 to 88 patients.

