For Arm 2B, same as the other two arms, if fewer than 13 patients are enrolled at the MTD, the phase II extension trial using Simon's two-stage Minmax design will require 26 patients to test the null hypothesis that the response rate at day 28 is <40% versus the alternative that the response rate is $\geq 65\%$ after assuming 80% power and a significance level of 0.05 and using a maximum of 26 patients. We expect that for each arm, phase I and II will require approximately 37 patients due to use of patients from the phase I trial in the phase II extension ([table 4](#) shows about 9 patients will be treated under MTD). But the sample size could be as high as 44 when only two patients were treated at MTD in phase I. We expected the sample size of phase I/II study for Arm 2B will be 37 to 44 patients.

The number of evaluable patients per year will be approximately 20 for each arm. We expect accrual to be completed within 7 years.

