13.4 Early Stopping Rule

During Phase I CRM, the trial will stop if the posterior probability that the lowest dose is more toxic than the target is greater than 90%. Stopping rules will also be employed to monitor excess toxicity outside of the phase I trial. Stopping rule was developed using Pocock stopping boundaries [32]. The stopping rule will be monitored for Arm 1, 2A and Arm 2B separately.

Early Stopping Rule for Toxicity

Stopping rules were developed for excessive Grade 4/5 non-hematologic, non-infectious toxicity attributed to the study drug occurring by day 28 after the last dose of hCG. The goal is to construct a boundary based on toxicity such that the probability of early stopping is at most 10% if the toxicity rate is equal to 20% and assuming 13 more patients of each arm are enrolled after phase I. Given these parameters, the upper stopping boundary for toxicity is 2 events out of 2 patients, 3 events out of 3 patients, 5 out of 8, or 6 at any time. If the true toxicity rate is as high as 50% then chance of early stopping is 80% and the expected sample size is 7.3.

14 Conduct of the Study

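### The printed phase II toxicity boundary is incomplete: for 13 patients at 50% toxicity it stops 74% of the time with expected size 8.7 to 8.8, not the stated 80% and 7.3

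*Combined protocol and SAP*

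**What the plan says.** Section 13.4 describes a Pocock-type boundary, applied to each arm separately, for Grade 4/5 non-hematologic, non-infectious toxicity attributed to the study drug up to day 28 after the last dose. The design target is a stopping probability of "at most 10% if the toxicity rate is equal to 20% and assuming 13 more patients of each arm are enrolled after phase I". The limits are then listed as "2 events out of 2 patients, 3 events out of 3 patients, 5 out of 8, or 6 at any time". Their performance is given in the next sentence: "If the true toxicity rate is as high as 50% then chance of early stopping is 80% and the expected sample size is 7.3".

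Section 13.2 gives the sample sizes. For Arm 2B: "We expected the sample size of phase I/II study for Arm 2B will be 37 to 44 patients". The upper figure arises because the size "could be as high as 44 when only two patients were treated at MTD in phase I". Section 13.2 gives the same upper figure of 44 per arm for Arms 1 and 2A, with about 33 expected. Phase I is 20 patients in each arm.

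**The concern.** Two faults can be seen in the list before any calculation. Three events in three patients cannot occur without two events in the first two, so the 3-of-3 limit is redundant. The list also goes from 3 events to 5 with no limit at 4. A boundary that requires nearly the same strength of evidence at every patient, as the Pocock method does, would not have such a gap.

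This matters because section 13.4 is the only numerical safety limit in phase II, and section 11.3 sends sites to it for stopping-rule events. Applied literally, the list lets an arm continue after 3 events in 4 patients (unless the first two patients both had one). It also continues after 4 events in 5 to 7 patients, and when the fifth event comes at patient 9, 10 or 11. The boundary that yields the protocol's own figures stops in each case. Event reporting within 24 hours and oversight by the monitoring council reduce the risk, but neither sets a number.

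**Working it through.** **Inputs** (section 13.4): 13 patients; tolerated toxicity 20% with at most 10% stopping; comparison toxicity 50% with stated stopping 80% and expected size 7.3; the printed limits.

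**Method.** Let f_n(x) be the probability that the arm is still open after n patients with x events. Then f_n(x) = (1−p)·f_{n−1}(x) + p·f_{n−1}(x−1). Any probability that reaches the limit at patient n is removed as s_n. P(stop) = Σ s_n, and E[N] = Σ n·s_n + 13·(1 − Σ s_n).

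**1. Where the plan's own figures come from.** Take 2 in 2, 3 within 4, 4 within 7, 5 within 11, or 6 at any time. At p = 0.5:

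| Patient n | 2 | 4 | 6 | 7 | 9 | 10 | 11 | 13 |
|---|---|---|---|---|---|---|---|---|
| s_n | 0.250 | 0.125 | 0.078 | 0.109 | 0.055 | 0.074 | 0.074 | 0.032 |

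P(stop) = 0.797 and E[N] = 4.69 + 13 × 0.203 = 7.33. At p = 0.2, P(stop) = 0.097. All three agree with the stated 80%, 7.3 and 10% cap. A search over all nested boundaries with 6 at any time and at most 10% stopping at 20% toxicity finds no other match. The boundary also behaves as a Pocock boundary should. At 20% toxicity every included point has a binomial tail of at most 0.0504 (5 of 11), and the next excluded points are 0.0563 (4 of 8), 0.0579 (3 of 5) and 0.0726 (5 of 12). The printed 3 of 3 and 5 of 8 are the first patients at which this boundary requires 3 and 5 events.

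**2. The printed list, p = 0.5.** This can be counted by hand over the 2^13 = 8,192 equally likely sequences:

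- six or more events in 13: 8,192 − (1 + 13 + 78 + 286 + 715 + 1,287) = 5,812
- at most five events, with the first two patients both events: sequences of 11 with at most 3 events = 1 + 11 + 55 + 165 = 232
- exactly five events, all in the first 8, first two not both events: C(8,5) − C(6,3) = 56 − 20 = 36

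P(stop) = (5,812 + 232 + 36)/8,192 = 6,080/8,192 = 0.742. E[N] is 8.72 if 5 of 8 means at any point up to patient 8, and 8.84 if it applies only at patient 8. At p = 0.2, P(stop) = 0.0655.

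**3. Other readings.** None gives the stated pair.

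- With 14 patients, stopping is 80.9% but E[N] is 9.0 to 9.1.
- With 12 patients, stopping is 66.5% and E[N] is 8.4 to 8.5.
- Holding each printed limit until the next one gives 84 to 90% stopping, E[N] 6.1 to 6.2, and 17 to 19% stopping at 20% toxicity, which breaks the cap.

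**4. Loss of early stopping, p = 0.5.** By patient 7 the printed list has stopped in 35.2% of trials (26.6% if 5 of 8 applies only at patient 8), and the full boundary in 56.2%. The two stop at the same patient only at patient 2 (0.250) and patient 13 (0.032). In 0.797 − 0.250 − 0.032 = 0.515 of trials, then, the printed list stops later or not at all: 0.797 − 0.742 = 5.5% not within 13 patients, and the remaining 46.0% later.

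**5. More than 13 further patients.** Arm 2B: 37 − 20 = 17 and 44 − 20 = 24. Stopping probability at 20% toxicity with full accrual:

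| Further patients | 13 | 14 | 15 | 16 | 17 | 24 |
|---|---|---|---|---|---|---|
| Printed list | 6.6% | 7.7% | 9.2% | 11.1% | 13.2% | 35.8% |
| Full 13-patient boundary | 9.7% | 10.4% | 11.6% | 13.1% | 15.0% | 36.3% |

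A favourable Arm 2B path from the section 13.2 table ("Enroll 13 more patients Next dose level 4: N = 2") has 2 patients at level 4 and at most 11 at level 5. If level 5 is the MTD, 26 − 11 = 15 more are needed. At 10% toxicity the printed list stops only 1.4% (17 patients) to 3.6% (24 patients) of the time.

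**The case against.** The strongest reply is that this is an abridged transcription of a correctly derived boundary. The 80%, the 7.3 and the cap are all right for that boundary, and the documents do not show which version is used in practice. That is probably how the error arose, but the protocol contains only the printed list.

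A second reply is that 50% drug-attributed Grade 4/5 toxicity is extreme, since the background section puts severe reactions below 1%. At lower rates the gap remains: 22.2% against 29.3% at 30% toxicity, and 47.9% against 56.0% at 40%. Most of the 51.5% is later rather than missed stopping, as shown above.

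Third, expected sample size assumes each outcome is known before the next patient starts. Toxicity is counted to day 28 after the last dose, and section 13.4 states no enrolment pause, so the difference of 1.4 to 1.5 patients is an idealised design figure and not a count of patients exposed. This stands.

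Fourth, the number of further patients is a separate and lesser matter. Thirteen is a declared assumption that fits 33 − 20 for Arms 1 and 2A. The inflation needs full accrual at exactly 20% toxicity, and it errs toward stopping. This also stands. The same issue would reach Arms 1 and 2A if they came near 44 patients.

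**Conclusion.** The concern holds. The limits in section 13.4 do not deliver the properties stated beside them: 74.2% stopping instead of 80%, and an expected size of 8.72 to 8.84 instead of 7.3, a difference of 1.4 to 1.5. This rests on 13 patients, independent outcomes at 50% toxicity, and assessment after every patient. The 10% cap is met at 13 patients. A safety limit whose text is weaker than its description must be corrected.

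The secondary point is conditional. With 17 to 24 further patients and true toxicity of exactly 20%, the printed list would stop 13.2 to 35.8% of the time, and the full 13-patient boundary 15.0 to 36.3%. Both numbers of patients are maxima, because stage 1 futility can end an arm at 12, and 24 arises only if two patients were treated at the MTD in phase I. This would expose no extra patients.

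**What to change.** 1. Make the list and its properties agree. Either print the complete boundary behind the stated figures (2 in 2, 3 within 4, 4 within 7, 5 within 11, or 6 at any time), or keep the printed list, delete the redundant 3-of-3 limit, say whether 5 of 8 applies only at patient 8 or at any point up to it, and restate the properties as 6.6%, 74% and 8.7 to 8.8. The choice is the sponsor's.
2. Once the number treated at the MTD is known, regenerate the boundary by the same method for each arm's remaining number and state its properties. The two steps belong together, because the full 13-patient boundary exceeds the cap from 14 patients on, whereas the printed list does so from 16. For 14, 15 and 16 further patients a re-derived boundary keeps 2 of 2 within the cap (9.8%, 9.8%, 9.5%). At 17 a strict re-derivation drops 2 of 2 (8.1% false stopping; 87% stopping and expected size 9.0 at 50% toxicity), while keeping it gives 10.1%, 87% and 8.2. The sponsor should state which it adopts.

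Step 1 costs a wording change in section 13.4, and in the OnCore stopping-rule form if that form carries the limits. Step 2 costs one calculation per arm and an amendment, which would be a disclosed change to a safety limit if 2 of 2 no longer applied. Neither needs extra patients or data.

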14.1 Good Clinical Practice

The study will be conducted in accordance with the appropriate regulatory requirement(s). Essential clinical documents will be maintained to demonstrate the validity of the study and the integrity of the data collected. Master files should be established at the beginning of the study, maintained for the duration of the study and retained according to the appropriate regulations.

14.2 Ethical Considerations

The study will be conducted in accordance with ethical principles founded in the Declaration of Helsinki. The IRB will review all appropriate study documentation in order to safeguard the rights, safety and well-being of the patients. The study will only be conducted at sites where IRB approval has been obtained. The protocol, consent, written information given to the patients, safety updates, annual progress reports, and any revisions to these documents will be provided to the IRB by the investigator.

